11.2 ADVERSE EVENT EVALUATION AND REPORTING

- ***AE Reporting***

Conditions or diseases which are pre-existing and chronic should not be recorded as adverse events. Changes in a chronic condition or disease that are consistent with natural disease progression are NOT considered adverse events. Pre-existing conditions or diseases should be documented as part of the subject's medical history.

Elective or pre-planned treatments for atrial fibrillation (e.g. scheduled re-ablation or cardioversion) which are part of the subject's scheduled treatment plan should not be considered adverse events. However, any events related to a procedure (including re-do procedures) or the patient's underlying atrial fibrillation which were not expected or indicate a worsening of condition should be reported as adverse events. (example: procedure-related perforation or cardiac tamponade).

Every effort should be made to report the underlying condition or unifying diagnosis for the event. The adverse event should be recorded in standard medical terminology rather than the subject's own words when possible. Signs

and symptoms that are considered unrelated to an encountered condition or disease should be recorded as individual adverse events (e.g. if congestive heart failure and severe headache are observed at the same time, each event should be recorded as an individual adverse event). In contrast, adverse events that occur secondary to other events (e.g. sequelae), if clearly identifiable, should be identified by the primary cause (example: bradycardia → dizziness → fainting; the primary adverse event is bradycardia).

- ***Relatedness***

The investigator will assess each adverse event for its relationship to the study device, and whether it was anticipated in the protocol. The determination of the level of relatedness of the adverse event to the study device or procedure will be made according to the definitions below

- Device Related: The adverse event was directly and clearly related to the device or procedure
- Not Device Related
- Unknown

Adverse events that are serious and/or unanticipated will be reviewed immediately by the Abbott EP (Topera) Medical Monitor and will also be reviewed during quarterly DSMB meeting.

- ***SAE Reporting***

All serious adverse events (SA(D)Es) should be phoned / faxed / e-mailed to Abbott EP (Topera, Inc.) within 24 hours of learning of an event. The following information will be collected and recorded as appropriate.

- Nature of adverse event
- Date of onset of adverse event
- Date of resolution of adverse event, if applicable
- Statement as to why it is considered unanticipated, if applicable
- Statement as to why it is considered serious, if applicable
- Statement as to the degree to which it is considered device related, and why
- Results of any diagnostic tests that were performed
- Description of any treatment administered

It is the responsibility of each Investigator to report all Serious Adverse Events and/or Serious Adverse Device Effects to the IRB/EC, according to national regulations and IRB/EC requirements.

Abbott EP (Topera Inc.) will assure that the Authorized Representative will report all Serious Adverse Events to the Competent Authorities in accordance with European Medical Devices directives and all applicable national regulations.

Any protocol modifications deemed necessary by this review will be reported to the IRB/EC and, for sites located outside of Europe, to the applicable Ministry of Health.

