7 ENDPOINTS

7.1 PRIMARY SAFETY ENDPOINTS

Safety shall be evaluated both acute (in hospital) and long term.

Table 1 – Primary Safety Endpoints

Endpoint	Description
Acute success	Freedom from serious adverse events related to the procedure within 7-10 days of the procedure.
Long-term success	Freedom from procedure-related serious adverse events (including those related to repeat procedures) within one year of the initial procedure.

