This endpoint will be evaluated using a Chi-Square test of independence, the proportions assumed to be binomial for each group.

C. Acute Safety (Primary safety endpoint)

The acute safety success of either treatment arm is defined as freedom from serious adverse events related to the procedure within ten (10) days of the index procedure. The proportion of successes in each arm will be calculated as follows:

$$\frac{n}{N}$$

Where:

n = the total count of subjects presenting freedom from serious adverse events related to the procedure within ten (10) days of the index procedure.

N = the total count of subjects in that arm in the ITT group

The statistical hypothesis for this endpoint is operationalized as follows:

$H_0: p_E = p_C$

$H_A: p_E \neq p_C$

Where:

p_E = the proportion of "successes" in the FIRM arm

p_C = the proportion of "successes" in the conventional ablation control arm

This endpoint will be evaluated using a Chi-Square test of independence, the proportions assumed to be binomial for each group.

D. Long-Term Safety (Primary safety endpoint)

Long-term safety is defined as freedom from procedure-related serious adverse events (SAEs) (including those related to repeat procedures) within one year of the initial procedure.

The statistical hypothesis for this endpoint is operationalized as follows:

$H_0: p_E = p_C$

$H_A: p_E \neq p_C$

$\alpha =$

Where:

p_E = the proportion of subjects free from serious adverse events related to the procedure (including from any repeat procedures required) within one year of the index procedure in the FIRM arm

p_C = the proportion of subjects free from serious adverse events related to the procedure (including from any repeat procedures required) within one year of the index procedure in the conventional ablation control arm

The proportion of events in each treatment arm shall be evaluated relative to their respective primary endpoint using both Chi-Square (Binomial, 1df) and by Kaplan-Meier survival estimation. Each evaluation will include 95% confidence intervals.

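### The only relatedness scale sets a high bar with no level for a possible or probable link, so such SAEs may be left out of both primary safety endpoints

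*Protocol*

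**What the plan says.** Section 7.1 makes two safety endpoints primary, and both depend on relatedness to the procedure. The long-term one is "Freedom from procedure-related serious adverse events (including those related to repeat procedures) within one year of the initial procedure". For the acute one, section 16.2 C defines the numerator of the success proportion as "the total count of subjects presenting freedom from serious adverse events related to the procedure within ten (10) days of the index procedure"; the denominator is every subject of that arm in the ITT group.

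Relatedness is defined once, in section 11.2. Its opening sentence names the device alone: "The investigator will assess each adverse event for its relationship to the study device". The next sentence says that the definitions cover relation to the device or the procedure. Three levels follow:

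- Device Related, defined as "The adverse event was directly and clearly related to the device or procedure";
- "Not Device Related", without further definition;
- *Unknown*, also without definition.

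Two other provisions bear on the point. The SAE report in section 11.2 must contain a "Statement as to the degree to which it is considered device related, and why". Section 13.5 gives a DMC independent review and the adjudication of endpoint events. Section 11.2 adds review of serious events by the sponsor's medical monitor and at quarterly DSMB meetings.

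**The concern.** The scale has one positive level with a demanding threshold, and nothing between it and a plain negative. An SAE that the investigator thinks may well be procedural, but cannot call clear and direct, has no place except *Unknown*. Section 11.3 lists anticipated events for which this could easily arise, such as stroke or TIA, thromboembolism, pulmonary vein stenosis and pleural effusion. Attribution becomes harder over the one-year window of the long-term endpoint.

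Three things are at stake. First, procedure-related SAE rates in both arms could be understated. Second, the tests in 16.2 C and D are tests of equality, so events lost from both arms reduce the ability to detect a difference in harm. Third, the first rating is made by the investigator and the protocol describes no masking (section 10.2 has the operator interpret the FIRM maps), so *Unknown* could be used more in one arm than in the other. The label adds to the difficulty: relation to the procedure is recorded under a device heading, which fits the conventional arm poorly because that arm has no FIRM-guided procedure.

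**Working it through.** The protocol states no safety rate or margin, and the sample-size section is blacked out, so there is no figure to reproduce. The check is a reading of the text, followed by illustrations on assumed rates.

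**Reading the text**

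1. In 16.2 C the success proportion is n/N, with N all ITT subjects in the arm. Each subject is therefore either a success or a failure.
2. A failure requires an SAE related to the procedure. The only definition of related in the protocol is the strict one in 11.2.
3. A possible or probable link is not clear and direct, and it is not absent. Only *Unknown* remains.
4. No section says how *Unknown* enters n. On a literal reading, a subject whose only SAE is *Unknown* has no related SAE and stays in n.
5. Adjudication (13.5) could change that, but it has no stated relatedness criterion. It is also not stated whether an *Unknown* SAE would reach the DMC as an endpoint event. The SAE narrative asks for degree, but about the device, and no rule links it to the endpoint.

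**Illustration 1: understatement of the rate**

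Observed rate = true rate × (1 − share rated *Unknown*). This treats every *Unknown* SAE as truly related and assumes that adjudication reclassifies none.

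- True rate 5%: 0.05 × 0.9 = 4.5%; 0.05 × 0.8 = 4.0%; 0.05 × 0.6 = 3.0%.
- True rate 3%, share 10% to 40%: 2.7% down to 1.8%.
- True rate 8%, share 10% to 40%: 7.2% down to 4.8%.
- True rate 5% in both arms, share 40% in one and 10% in the other: 3.0% v 4.5%. With 350/2 = 175 per arm (the maximum under section 6.1), that is about 5 v 8 subjects. The pooled proportion is 13/350 = 0.0371, the standard error √(0.0371 × 0.9629 × 2/175) = 0.0202, and z = (3/175)/0.0202 = 0.85, so p is about 0.40.

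**Illustration 2: effect on the comparison**

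Uncorrected chi-square test, 1 df, 175 per arm. Clearly related SAEs are equal in the two arms (5, 9 or 14 subjects, about 3%, 5% or 8%). *Unknown* SAEs occur in 4 control subjects (about 2%) and in 4, 9 or 14 FIRM subjects (about 2%, 5% or 8%). With *Unknown* left out, the arms are identical and p = 1.00 throughout. With *Unknown* counted as an event:

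| Clearly related, each arm | *Unknown*, FIRM v control | Success, FIRM v control | p |
|---|---|---|---|
| 3% | 2% v 2% | 94.9% v 94.9% | 1.00 |
| 3% | 5% v 2% | 92.0% v 94.9% | 0.28 |
| 3% | 8% v 2% | 89.1% v 94.9% | 0.049 |
| 5% | 2% v 2% | 92.6% v 92.6% | 1.00 |
| 5% | 5% v 2% | 89.7% v 92.6% | 0.35 |
| 5% | 8% v 2% | 86.9% v 92.6% | 0.078 |
| 8% | 2% v 2% | 89.7% v 89.7% | 1.00 |
| 8% | 5% v 2% | 86.9% v 89.7% | 0.41 |
| 8% | 8% v 2% | 84.0% v 89.7% | 0.114 |

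With equal use of *Unknown*, both arms fall by 4/175 = 2.3 points and the difference between them stays at zero. The scoring alters the comparison only when *Unknown* is unevenly split, and here p falls below 0.05 only in the most uneven split combined with the lowest clearly related rate.

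**The case against.** A reader might infer that the protocol scores possibly related SAEs as safety successes, so that every uncertain event is resolved in favour of safety. The documents do not support that. No section assigns *Unknown* to success, and neither 7.1 nor 16.2 cites the scale in 11.2. Serious events are reviewed by the medical monitor and the DSMB, endpoint events go to a DMC described as independent, and each SAE report carries a reasoned statement of degree. Some possibly related events may well be recovered this way.

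A second objection is that the scoring of an indeterminate category commonly belongs in the SAP, which is not at hand. That stands for the scoring of *Unknown*. It does not stand for the scale, which is fixed at data collection: an SAP can assign *Unknown* to one side, but it cannot recover gradings that sites were never offered or undo a threshold that investigators have already applied.

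Third, all the magnitudes are assumed, and uneven use of *Unknown* is a possibility, not something the protocol shows. This stands in full. The 3.0% v 4.5% example would not change a test result at this sample size.

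Fourth, counting every *Unknown* SAE as a primary event for a full year would bring in background events, for example a late stroke in a population with atrial fibrillation. This also stands, and it is the reason to keep that rule to a sensitivity analysis.

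**Conclusion.** The point holds as a cheap improvement. A stated threshold, and not merely a gap, places possibly or probably procedure-related SAEs outside the only category that plainly feeds the two primary safety endpoints. The existing safeguards may return some of them, but without a relatedness criterion or a rule on whose classification counts.

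The size is not derivable from the protocol. Under assumed true rates of 3% to 8% with 10% to 40% of events rated *Unknown* and none reclassified, the endpoint would show between 1.8% and 7.2%. Understatement needs only that some truly related events are rated *Unknown* and stay there. Bias between arms needs uneven use as well, and nothing in the protocol shows that this will occur.

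**What to change.** In section 11.2:

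- rate relation to the procedure separately from relation to the device, for both arms;
- define related as at least a reasonable possibility of a causal relation, so that possible and probable are included.

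In section 16.2 C and D:

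- count SAEs classified as procedure-related under that definition;
- state that the DMC-adjudicated classification governs the analysis;
- prespecify a sensitivity analysis in which SAEs still *Unknown* after adjudication count as events;
- show two supportive tables: all SAEs within 10 days whatever their relatedness, and the endpoints under the present narrow definition.

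The cost is a few sentences and a second relatedness item on the adverse event form, with no added visits or subjects. SAEs already reported would have to be re-rated. Reported safety rates become slightly less favourable, and some background events may be counted, mainly in the one-year endpoint.

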11.3 ANTICIPATED ADVERSE EVENTS

Table 9 – Anticipated Adverse Events

Description	Description
Discomfort due to insertion/removal of vascular sheaths beyond what is normally observed	Ventricular arrhythmia requiring defibrillation
Hemorrhage and/or hematoma at sheath insertion requiring evacuation or transfusion	Cardiac tamponade due to perforation
Extremity weakness, swelling, and/or pain	
Discomfort and/or damage to the skin, muscles, or nerves due to remaining in a supine position for an extended period of time.	Nerve injury (diaphragmatic paralysis, pyloric spasm, gastric hypomotility)
Complete AV block	Air embolism
Nausea /vomiting	Allergic reaction
Headache different from baseline	Endocarditis
Hypertension >180 mm Hg systolic (repeated measures)	Esophageal-atria fistula
Hypotension <80 mm Hg systolic (repeated measures)	Hemothorax
Brief “black out” periods	Pericarditis
Shortness of breath/Dyspnea	Pseudo aneurysm
Feeling of chest pain, skipped beats, and/or rapid heart rate different from baseline	Pulmonary vein stenosis
Damage to skin from prolonged exposure to x-rays	Radiation injury
New arrhythmias (not previously documented)	Renal failure from IV contrast

Arterial injury requiring intervention	Respiratory failure
Thromboembolism	Stroke/TIA
Local/systemic infection	Valvular damage
Pneumothorax	Pleural effusion
AV fistula	Pulmonary edema
Thrombophlebitis	Anemia requiring transfusion
Pulmonary embolism	Vasovagal reaction
Myocardial infarction	New pericardial effusion >1 cm
Discomfort and/or damage to the skin, muscles, or nerves due to percutaneous access in excess of usual	Death (must be reported within the regulation of serious adverse events)
Left heart access via trans-septal puncture has known potential adverse events of: cardiac perforation, cardiac tamponade, and embolic events*.	

* Literature reviews have demonstrated that the risk of such events are <1%. Mullins, Charles E. "Trans-septal left heart catheterization: Experience with a new technique in 520 pediatric and adult subjects." *Pediatric Cardiology*, v. 4, pgs. 239-246 (1983).

11.4 DEVICE DEFICIENCIES AND MALFUNCTIONS

Investigators must report all possible device deficiencies, malfunctions or near incidents associated with the device, per institutional standard practice and regulations. This includes unexpected outcomes or device deficiencies that might have led to a serious adverse event if a) suitable action had not been taken or b) intervention had not been made or c) if circumstances had been less fortunate.

- **Definitions**

- Device deficiency - inadequacy of a medical device related to its identity, quality, durability, reliability, safety or performance, such as malfunction, misuse or use error and inadequate labeling (EN ISO/FDIS 14155:2010).
- Malfunction - failure of an investigational medical device to perform in accordance with its intended purpose when used in accordance with the instructions for use or protocol (EN ISO/FDIS 14155:2010).

12 INVESTIGATOR REQUIREMENTS

12.1 PROTOCOL ADHERENCE

Each Investigator must adhere to the protocol as detailed in this document and agree that the Sponsor must approve any change to the protocol before seeking approval from the IRB/EC or CA. Each Investigator will be responsible for enrolling only those subjects who have met all of the protocol inclusion criteria and none of the exclusion criteria.

12.2 ELECTRONIC CASE REPORT FORMS AND DATA CAPTURE SYSTEM

Data collection will involve the use of the Electronic Data Capture (EDC) system, to which only authorized personnel will have access. Electronic case report forms (eCRFs) will be used to capture study data in an EDC system. Entering of eCRFs should be handled in accordance with instructions from the Sponsor or Sponsor representative. All eCRFs must be completed by qualified study center personnel. Each Investigator is responsible for ensuring that accurate data are entered into the EDC system in a timely manner.

The Investigator or designee will be responsible for reviewing eCRFs, resolving data queries generated by the Sponsor via the system, providing missing or corrected data, approving all changes performed on the subject data, and endorsing these data within the EDC system. This approval method will include applying an electronic signature, a uniquely assigned user name, and a password that together will represent a traditional handwritten signature.

Queries may be issued electronically to the study site and answered electronically by that site's personnel. The identifying information (assigned user name, date, and time) for both the originator of the query and the originator of the data change (if applicable) will be collected.

12.3 SOURCE DOCUMENT MAINTENANCE

Source documents may include, but are not limited to, study progress notes, study- or subject-specific e-mail correspondence, computer printouts, laboratory data, and recorded data from automated instruments. The original signed ICF for each participating subject shall be filed with records kept by the Investigator. All documents produced in this study will be maintained by the Investigator and made available for inspection by the Sponsor or Sponsor representative and applicable regulatory authorities.

12.4 STUDY MONITORING REQUIREMENTS

The Sponsor or Sponsor representative will conduct site visits to inspect study data, subjects' medical records, and eCRFs in accordance with current ICH E6 Good Clinical Practice (GCP) guidelines, and the respective United States or foreign regulations and guidelines, as applicable. The Sponsor or Sponsor representative will also be able to review query status remotely, which may warrant additional

communication with the Investigator and the study site's personnel. The Investigator will make available to the Sponsor, or Sponsor representative, source documents, signed ICFs, and all other study-related documents. The Investigator will allow the Sponsor or Sponsor representative and applicable regulatory authorities to inspect facilities and records relevant to this study.

12.5 STUDY COMPLETION

The Sponsor requires the following data and materials before a study can be considered complete or terminated, including, but not limited to:

- Laboratory findings, clinical data, and all special test results from screening through FU
- eCRFs properly completed by appropriate study personnel and signed and dated by the Investigator within the EDC system. This approval method will include applying an electronic signature, a uniquely assigned user name, and a password that together will represent a traditional handwritten signature.
- Copies of complete device accountability records, if applicable
- Copies of all IRB/IEC or CA approvals and acknowledgements
- A summary of the study prepared by the Investigator (an IRB/IEC or CA summary letter is acceptable)

13 STUDY MANAGEMENT

Study management will occur in accordance with ISO 14155, (Clinical investigation of medical devices for human subjects – Good clinical practices), the Declaration of Helsinki, the applicable national regulations and Institutional research policies and procedures. Several key components of study management are discussed separately below.

13.1 IRB/IEC OR COMPETENT AUTHORITY APPROVAL

The IRB/IEC or CA must approve the protocol or amended protocol (if applicable) and the corresponding ICF before the study may be initiated; any recruiting materials before use; and subsequent amended protocols and corresponding ICFs before instituting amendment-specified changes to the study, unless required for subject safety.

The Investigator is responsible for informing the IRB/IEC or CA of any changes made to the protocol, and to advise the IRB/IEC or CA, at least once a year, about the progress of the study. The Investigator (or Sponsor, if applicable) is also responsible for notifying the IRB/IEC or CA of any significant AEs that occur during the study according to local IRB/IEC or CA requirements.

- **Study Registration**

The study will be registered with www.clinicaltrials.gov in accordance with the Declaration of Helsinki.

13.2 MONITORING

The study will be monitored periodically at each enrolling site per the study monitoring plan for the purposes of

- Verifying compliance to the protocol and applicable regulations,
- Verifying case report form data to original entries in source files,
- Abbott EP (Topera) employees or representatives will monitor the study according to company standard operating procedures.

13.3 STUDY AUDITS

The Sponsor and representatives of regulatory health authorities are permitted to inspect the study documents (protocol, case report forms, study-related medical records, study correspondence with EC and sponsor, etc.). In addition to ongoing monitoring of the study, GCP audits by the Sponsor or its representatives are also permitted. All attempts will be made to preserve subject confidentiality.

13.4 PROTOCOL DEVIATIONS

A protocol deviation is defined as any event where the clinical investigator or site personnel did not conduct the study according to the protocol.

Investigators can only initiate deviations from the protocol where necessary to protect the life or physical wellbeing of a subject, i.e., in an emergency. Protocol deviations shall be reported to the Sponsor regardless of whether medically justifiable, pre-approved by the Sponsor, or taken to protect the subject in an emergency. Subject-specific deviations will be reported on the eCRF. Non-subject specific deviations, (e.g., unauthorized use of a study device by a physician who has not signed an investigator agreement, etc.), will also need to be reported to the Sponsor. All deviations, regardless of major / minor or pre-approved, will be reported on the eCRF. Investigators will also adhere to procedures for reporting study deviations to their IRB/EC in accordance with their specific IRB/EC reporting policies and procedures.

Regulations require that investigators maintain accurate, complete and current records, including documents showing the dates of and reasons for each deviation from the protocol.

- **Definitions**

For reporting purposes, the Sponsor classifies study deviations as major or minor:

- Major deviation: Any deviation from subject inclusion and exclusion criteria; subject informed consent procedures (e.g., failure to obtain informed consent or failure to obtain informed consent prior to study entry); randomization errors; failure to report SAE's, unanticipated adverse device effects, and deaths within applicable regulatory timeframes; device accountability issues (e.g., missing or lost investigational product); or device misuse / unauthorized device use.
- Minor deviation: Deviation from a protocol requirement such as incomplete/ inadequate subject testing procedures, non-compliance with medication regimens, follow-ups performed outside specified time windows, etc.

The Sponsor will continuously monitor site compliance. The site will receive a list of site-specific study deviations on an annual basis as part of the Annual Progress Report and as part of the Final Report upon completion of the study.

